11.8.1.1 Hypoglycemic AEs based on documentation on the Hypoglycemia CRF page
Hypoglycemic AEs which are only documented on the CRF AE page and for whom the CRF Hypoglycemia page is blank or missing will not be considered in the analyses which are described below.

An additional breakdown of hypoglycemic TEAEs categorized by maximum CTCAE and ADA grade within each SOC and preferred term will be provided (Table 6, Analyses 4 - 8). The analysis will be done for hypoglycemic AEs measured with test methods "Fingerstick" and "Venous Blood Draw" (Table 6, Analyses 5 and 7). Events graded using lowest blood glucose values with test method "Other" will be presented separately (Table 6, Analyses 6 and 8). For this analysis the CTCAE and ADA grades will be derived using information documented on the Hypoglycemia page. Grading will be based on mmol/L unit (mg/dL values will be converted to mmol/L before grading).

Table 7: CTCAE grades for Hypoglycemia (based on lowest blood glucose values documented on the Hypoglycemia page)

SOC	AE Term	Grade 1	Grade 2	Grade 3	Grade 4
Metabolism and nutrition disorders	Hypoglycemia	<3.9 and ≥ 3.0 mmol/L	<3.0 and ≥ 2.2 mmol/L	<2.2 and ≥ 1.7 mmol/L	<1.7 mmol/L;

Table 8: ADA grades for Hypoglycemia (based on lowest blood glucose values and intervention information documented on the Hypoglycemia page)

SOC	AE Term	Grade 1	Grade 2	Grade 3
Metabolism and nutrition disorders	Hypoglycemia	<3.9 and \geq 3.0 mmol/L	<3.0 mmol/L	A severe event characterized by altered mental and/or physical status requiring assistance selected by "Was third party intervention required for this episode of hypoglycemia?" is Yes

On the Hypoglycemia CRF page further details are documented if the answer to the question "Is this a hypoglycemic event?" on the Adverse Event CRF page is Yes. Hypoglycemic TEAEs will be reported using data recorded on both the Adverse Event page and the Hypoglycemia page as follows:

- Severe Hypoglycemia (Table 6, Analysis 9)
- Symptomatic Hypoglycemia (Table 6, Analysis 12)
- Measured Hypoglycemia (Table 6, Analysis 12)

A summary of ADA severe hypoglycemia TEAEs, symptomatic hypoglycemia TEAEs and measured hypoglycemia TEAEs will be produced, presenting the number and percentage of subjects with at least one event, as well as of the number and percentage of subjects with no events, at least one event, 1 event, 2 events, and 3 or more events (Table 6, Analysis 15). Persistent and non-persistent TEAEs will be summarized, presenting subjects with no event and at least one event (Table 6, Analysis 12).

Symptomatic or measured hypoglycemic TEAEs will be summarized by site, treatment group and overall, presenting the number of events reported, the number and percentage of subjects with at least one event (Table 6, Analysis 13). Sites with fewer than 8 subjects will be combined for summaries and analyses. A further summary by treatment group and overall will report the number and percentage of subjects with no events, at least one event, 1 event, 2 events, and 3 or more events (Table 6, Analysis 12).

All hypoglycemic events recorded on the Hypoglycemia CRF page will be listed for subjects in the SS. Additionally summary of ADA graded hypoglycemic event and TEAE by ERIPD subgroup will be produced for per protocol analysis set 2 and 3 (Table 6, Analysis 16).

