7.3 Safety

1) American Diabetes Association (ADA) Severe Hypoglycemic AE

A hypoglycemic AE will be classified as "ADA severe" if the answer to the question "Was third party intervention required for this episode of hypoglycemia?" is Yes on the Hypoglycemia CRF page as mentioned in the ADA hypoglycemia position statement (3).

ADA Severe Hypoglycemic AE should not be confused with hypoglycemia AEs that are graded severe (Grade 3) per National Cancer Institute Common Terminology Criteria for Adverse Events (NCI CTCAE) grade (see Section 11.8.1.1).

2) Adverse Event Leading to Discontinuation of IP

An AE will be classified as an AE leading to discontinuation of IP if the answer to the question "Did the adverse event cause the subject to be discontinued from the study?" is Yes on the AE CRF page.

3) Hypoglycemic AE

An AE will be classified as a hypoglycemic AE if the answer to the question "Is this a hypoglycemic event?" is Yes on the AE CRF page.

4) Injection Site Reactions

Injection site reactions will be identified using the High Level Term = "Injection site reactions".

5) IP-related adverse events

An AE will be classified as related to IP if the relationship to study treatment is Possibly Related, Probably Related, or Definitely Related. Additionally, if the relationship is missing, then the AE will be deemed related to IP.

6) Measured Hypoglycemic AE

A hypoglycemic AE will be classified as measured if the lowest blood glucose value documented on the Hypoglycemia page is less than or equal to 3.0 mmol/L.

7) Persistent/Non-persistent Hypoglycemic AE

Hypoglycemic event with Time in hypoglycemia (see definition in Section 7.4) greater or equal to an hour (per CGM) would be classified as persistent. A hypoglycemic event with Time in hypoglycemia below an hour (per CGM) would be classified as non-persistent.

8) Symptomatic Hypoglycemic AE

A Hypoglycemic AE will be classified as symptomatic if the answer to the question "Was subject aware of symptoms?" is Yes on the Hypoglycemia CRF page.

9) Treatment-emergent adverse events (TEAE)

A TEAE is defined as an AE occurring on or after the date of the subject's first dose of IP and on or before the day of last dose for AEs but not more than 30 days after the subject's last dose of IP for SAEs.

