A summary of events reported, categorized by maximum National Cancer Institute Common Terminology Criteria for Adverse Events (NCI CTCAE) severity grade as reported in the CRF will also be provided. Subjects with multiple events within a particular SOC or preferred term will be counted under the category of their most severe event within that SOC or preferred term. Sorting will be in descending frequency for SOC and descending frequency for preferred term within SOC in the total column.

Subject incidence of the following TEAEs will be tabulated by preferred term in descending order of frequency in the total column:

- Grade \geq 3 AEs
- Hypoglycemic AEs
- Severe hypoglycemic AEs
- IP-related AEs
- Grade \geq 3 IP-related AEs
- AE leading to discontinuation of IP
- IP-related AE leading to discontinuation of IP
- Injection site reactions

Sponsor: Gan & Lee Pharmaceuticals, USA Corporation
Protocol no: GL-GLAT2-3002

Statistical Analysis Plan
Version Date: 16-Nov-2020

A forest plot of the difference in incidence rates and CIs of TEAEs preferred terms with a $\geq 5\%$ difference in incidence between groups will be summarized. The 90% CIs will be computed using Wald method for risk difference without continuity correction.

Additionally, the hypoglycemia event rate will be compared between treatment groups using a negative binomial regression model (Table 6, Analysis 14). The response variable in the model will be the number of hypoglycemia events. The model will include factors for treatment group and site. In this study, sites were found to use variable procedures in their determination, collection and recording of the number of hypoglycemia episodes for individual subjects. So, to account for this additional variation, SITE is planned to be included as a fixed factor in the negative binomial regression model. This model will allow estimation of the site-adjusted, two-sided, 95% confidence interval of the treatment contrast. If that CI includes zero, we will conclude that this study does not provide sufficient evidence that subjects on this biosimilar have different numbers of hypoglycemic episodes compared to those on the reference analogue. The logarithm (to base e) of the follow-up time will be used as an offset variable in the model to adjust for subjects having different exposure times. The estimated treatment effect and the corresponding 95% confidence interval (CI), as well as the 2-sided p-value will be presented.

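### SAP 11.8.1.1 drops hypoglycemic AEs that have no Hypoglycemia page, so its type and grade tables show an unknown type or severity as absence of that type

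*SAP*

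**What the plan says.** Two CRF pages are involved. SAP 7.3, definition 3, begins "An AE will be classified as a hypoglycemic AE if the answer to the question" and then names a single question on the AE page. A Yes there makes the AE hypoglycemic, and no Hypoglycemia page is needed.

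The types are defined differently. In SAP 7.3, ADA-severe (third-party intervention), symptomatic (subject aware of symptoms) and measured (lowest glucose at or below 3.0 mmol/L) are all taken from fields on the Hypoglycemia page. For the grade tables, "the CTCAE and ADA grades will be derived using information documented on the Hypoglycemia page".

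SAP 11.8.1.1 opens with the exclusion: hypoglycemic AEs found only on the AE page and "for whom the CRF Hypoglycemia page is blank or missing will not be considered in the analyses which are described below". Below that sentence come:

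- the grade tables;
- the severe, symptomatic and measured events, introduced by "Hypoglycemic TEAEs will be reported using data recorded on both the Adverse Event page and the Hypoglycemia page as follows";
- the by-site summary of symptomatic or measured events;
- tables that give the "number and percentage of subjects with no events, at least one event, 1 event, 2 events, and 3 or more events".

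The section describes no category for AEs without a page, no count of them and no sensitivity analysis.

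**The concern.** A blank detail page means that the type and severity of an event are not known. It does not show that the event was not severe or not symptomatic. A table that leaves the event out and also has a row for subjects with no events turns missing information into the favourable answer.

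Three things make this worth correcting:

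- Hypoglycemia is the only adverse event of special interest (Protocol 11.3) and the first subgroup named in the secondary safety endpoint (Protocol 8.7.3.2).
- The SAP usually resolves missing data the other way. For causality, "if the relationship is missing, then the AE will be deemed related to IP". A missing Week 12 or Week 26 antibody sample counts as treatment-induced AIA (SAP Table 4), and a missing Week 26 value counts as glycemic control not achieved (SAP 11.7.2.1).
- SAP 11.8.1 states that "sites were found to use variable procedures in their determination, collection and recording of the number of hypoglycemia episodes for individual subjects". In an open-label trial, blank pages that differ by site or by arm are therefore plausible, although the SAP does not report them.

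At stake is whether a reader can trust the rows for severe, symptomatic and measured hypoglycemia, and whether the hypoglycemia tables agree with one another.

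**Working it through.** The documents state no figure for this point, so there is none to reproduce. The check traces the rule through the tables and then illustrates its size on assumed inputs.

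**Step 1. Which outputs fall under the rule** (numbers are the analyses in SAP Table 6)

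| Output | Described in | Under the rule? |
|---|---|---|
| Overall TEAE summary (3) | 11.8.1 | No |
| TEAEs by maximum CRF-reported grade | 11.8.1 | No |
| Negative binomial event-rate model (14) | 11.8.1 | No |
| General TEAE listing | 11.8.1 | No |
| Serious hypoglycemic TEAEs (10, 11) | 11.8.2 | No |
| CTCAE and ADA grade tables (5 to 8) | 11.8.1.1 | Yes |
| By-site symptomatic or measured (13) | 11.8.1.1 | Yes |
| ADA-severe, symptomatic, measured counts (15) | 11.8.1.1 | Yes |
| By preferred term (4), severe (9), hypoglycemia summary (12) | 11.8.1 in Table 6, but cited in 11.8.1.1 | Unclear |

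The dedicated hypoglycemia listing covers only events recorded on the Hypoglycemia page, so these AEs are absent there too.

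**Step 2. Where a subject lands**

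- All hypoglycemic AEs lack the page: the subject is in the *no events* row for every type.
- Some AEs are documented and some lack the page: the subject may sit in a lower count row. If no documented event is of the type, the subject is in *no events* for that type, although one event is unknown.
- The page is partly filled: the sentence does not exclude the AE, because it covers only blank or missing pages.

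**Step 3. Illustration of size**

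Let *p* be the true share of subjects with an event of the tabulated type, and *m* the share of those subjects whose events of that type all lack the page. Neither is in the documents; the values below are assumptions. The arm size of 275 is the planned number (SAP 5.1).

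Tabulated incidence = p × (1 − m). Subjects moved to *no events* = 275 × p × m.

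| p | m | Tabulated | Moved per arm |
|---|---|---|---|
| 20% | 5% | 19% | 2.75 |
| 40% | 5% | 38% | 5.5 |
| 40% | 10% | 36% | 11 |
| 40% | 20% | 32% | 22 |
| 60% | 20% | 48% | 33 |

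If the missing share differs by arm:

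- Equal true rates of 40%, with m of 5% in one arm and 15% in the other: 0.40 × 0.95 − 0.40 × 0.85 = 0.38 − 0.34 = 4 percentage points that are not real.
- True rates of 45% (test) and 40% (reference), with m of 15% and 5%: 0.45 × 0.85 − 0.40 × 0.95 = 0.3825 − 0.38 = 0.25 points tabulated, against a true 5.

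**Step 4. The one completeness figure in the documents**

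SAP 10.3 puts irreconcilable data points in fewer than 1% of subjects. On the planned 550, 0.01 × 550 = 5.5, so at most 5 subjects. If that figure covered every blank Hypoglycemia page, at most 5 subjects would move across both arms (5/275 = 1.8 points if all were in one arm). SAP 10.3 does not say whether blank pages are included.

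**The case against.** The strongest reply is that the main hypoglycemia results are untouched. The exclusion reaches only what is described below it, in a section whose title says that it rests on the Hypoglycemia page. An AE without a page is still counted in the overall TEAE summary, graded as reported on the CRF, entered in the negative binomial model, shown among serious events if serious, and listed. That stands. A reader might infer that hypoglycemia is understated throughout, or that the between-arm comparison is biased. The documents do not support this: the planned test of the event rate is described before the exclusion, and the affected tables are mostly descriptive.

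It also stands that the *no events* rows are type-specific. A fully documented, asymptomatic value of 3.5 mmol/L also belongs in that row for measured events, so the row does not declare a subject free of hypoglycemia.

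The comparison with missing causality is imperfect. There, one attribute of a counted AE is filled in; here the AE is counted elsewhere and its type is withheld. But the affected tables do not show the type as withheld. They show none.

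The size may well be small. Protocol 11.3 has the data system prompt for details when hypoglycemia is entered, and SAP 10.3 points the same way. Clustering of blank pages by site is an inference, since SAP 11.8.1 speaks of variable recording of episodes and does not mention missing pages. Finally, the table shells are a separate document (SAP Appendix 3) and may hold a footnote or a missing row.

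**Conclusion.** The point holds for the type, grade and type-specific count tables of SAP 11.8.1.1, and only there. In them, unknown type or severity is displayed as absence. The clearest case is ADA-severe hypoglycemia, which SAP 7.3 defines from the Hypoglycemia page alone. If such events are rare, a few subjects could change that row noticeably.

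The size cannot be stated from the documents. The range of about 3 to 33 subjects per arm rests wholly on assumed incidence (20 to 60%) and assumed page-less share (5 to 20%), and should not be read as an estimate. No primary or key secondary conclusion depends on this. A separate defect is certain: Table 6 and 11.8.1.1 disagree on whether Analyses 4, 9 and 12 fall under the exclusion, so hypoglycemia tables in the same report may not agree. This is a cheap improvement.

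**What to change.** 1. Replace the exclusion sentence in SAP 11.8.1.1 with a rule such as: *Hypoglycemic AEs with a blank or missing Hypoglycemia page are kept in these tables in a separate category, type/grade not determined (page missing). A subject with such an AE and no documented event of the type is shown in that category and not under no events.* An AE without a page should not simply be added to every any-event row, because that would assert that it was severe, symptomatic and measured at once.
2. Report the number of such AEs, and of subjects with them, by arm and by site.
3. Add one sensitivity row that counts them as events of the type. For ADA-severe, count them only when the AE is serious or CRF grade 3 or higher.
4. Reconcile Table 6 with 11.8.1.1 for Analyses 4, 9 and 12.
5. Leave Analysis 14 as it is, since it is not under the rule.

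The cost is SAP wording, one extra category and one extra row in the affected tables, all from data already held. Displayed rates may become slightly less favourable.

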11.8 Safety Analyses

Most safety analyses will be performed on the safety analysis population based on subject's actual treatment received.

A listing of planned summaries and analyses evaluating hypoglycemic events along with corresponding analysis plan section references is provided in Table 6.

Table 6: Listing of hypoglycemic event summaries and analyses

Analysis description	Section Reference	Tables Associated
1. Retrospective Summary of Continuous Glucometer Monitoring (CGM): Hypoglycemia Events	Section 11.7.3.1	Table 14.3.3.4.1
2. Retrospective Analysis of Continuous Glucometer Monitoring (CGM): Time in Hypoglycemia/Hyperglycemia	Section 11.7.3.2	Table 14.3.3.4.2
3. Overall Summary of Treatment-Emergent Adverse Events	Section 11.8.1	Table 14.3.2.1
4. Hypoglycemic Treatment-Emergent Adverse Events by Preferred Term	Section 11.8.1	Table 14.3.2.5

Analysis description	Section Reference	Tables Associated
5. Hypoglycemic Treatment-Emergent Adverse Events by System Organ Class, Preferred Term, and Maximum CTCAE Grade (based on lowest blood glucose values measured by fingerstick or venous blood draw)	Section 11.8.1.1	Table 14.3.2.6.1
6. Hypoglycemic Treatment-Emergent Adverse Events by System Organ Class, Preferred Term, and Maximum CTCAE Grade (based on lowest blood glucose values measured by test method equal "Other")	Section 11.8.1.1	Table 14.3.2.6.2
7. Hypoglycemic Treatment-Emergent Adverse Events by System Organ Class, Preferred Term, and Maximum ADA Grade (based on lowest blood glucose value measured by fingerstick or venous blood draw)	Section 11.8.1.1	Table 14.3.2.6.3
8. Hypoglycemic Treatment-Emergent Adverse Events by System Organ Class, Preferred Term, and Maximum ADA Grade (based on lowest blood glucose values measured by test method equal "Other")	Section 11.8.1.1	Table 14.3.2.6.4
9. Severe Hypoglycemic Treatment-Emergent Adverse Events by Preferred Term	Section 11.8.1	Table 14.3.2.7
10. Serious Hypoglycemic Treatment-Emergent Adverse Events by Preferred Term	Section 11.8.2	Table 14.3.2.13
11. IP-Related Serious Hypoglycemic Treatment-Emergent Adverse Events by Preferred Term	Section 11.8.2	Table 14.3.2.14
12. Summary of Hypoglycemic Treatment-Emergent Adverse Events	Section 11.8.1	Table 14.3.3.2.17
13. Summary of Symptomatic or Measured Hypoglycemic Treatment-Emergent Adverse Events by Site	Section 11.8.1.1	Table 14.3.3.2.18
14. Analysis of Hypoglycemic Treatment-Emergent Adverse Events	Section 11.8.1	Table 14.3.3.2.19

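### ADA Grade 3 hypoglycemia is defined by third-party help, but the two ADA-grade tables (SAP Table 6, Analyses 7 and 8) admit events by glucose test method, so their Grade 3 can fall below the ADA-severe count in Analysis 15

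*SAP*

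**What the plan says.** SAP 11.8.1.1 describes a breakdown of hypoglycemic TEAEs by maximum CTCAE and ADA grade and sets the events that enter it. For Analyses 5 (CTCAE) and 7 (ADA) it states: "The analysis will be done for hypoglycemic AEs measured with test methods", and names fingerstick and venous blood draw. Events whose lowest glucose value came from test method Other are shown separately, in Analyses 6 (CTCAE) and 8 (ADA). SAP Table 6 repeats the restriction in its titles. The title of Analysis 7 includes "Maximum ADA Grade (based on lowest blood glucose value measured by fingerstick or venous blood draw", and that of Analysis 8 makes the same tie to test method Other.

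The ADA scale itself is in SAP Table 8. Grades 1 and 2 are glucose ranges. Grade 3 is not: it is "A severe event characterized by altered mental and/or physical status requiring assistance selected by" a Yes to the third-party-intervention question on the Hypoglycemia CRF page. SAP 7.3 defines ADA severe the same way: "A hypoglycemic AE will be classified as 'ADA severe' if the answer to the question" on third-party intervention is Yes.

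Other severe-hypoglycemia outputs have no test-method condition: the overall TEAE summary (SAP 11.8.1), severe hypoglycemic TEAEs by preferred term (Analysis 9), the ADA-severe summary (Analysis 15) and the listing of Hypoglycemia-page events (SAP 11.8.1.1).

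**The concern.** The rule for entering the table and the rule for grading within it rest on different facts. Selection depends on how glucose was measured; the top grade depends on whether someone else had to help. For CTCAE grades (SAP Table 7), which rest on glucose alone, selection by test method is coherent. For ADA grades it is not, because an event can reach the highest grade without any glucose reading.

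Unmeasured events are plausible in this trial. SAP 6.3.2 lists symptomatic subject report as a source of hypoglycemia data alongside the central laboratory, the glucometer and CGM. SAP 11.8.1 says that sites varied in how they determined, collected and recorded episodes.

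At stake is agreement between tables on the protocol's adverse event of special interest (Protocol 11.3). A reader who compares Grade 3 in the maximum-grade tables with the ADA-severe count in Analysis 15 could find two different numbers under the same definition, with nothing in the SAP to explain the gap.

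**Working it through.** The plan gives no figure for this point, so there is nothing to reproduce. The check applies the SAP's own rules to each kind of event.

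Inputs:
- Grade 3 rule: third-party intervention = Yes, no glucose condition (SAP Table 8; the same test for ADA severe in SAP 7.3).
- Grades 1 and 2: lowest glucose below 3.9 and at least 3.0 mmol/L, and below 3.0 mmol/L (SAP Table 8).
- Entry to Analysis 7: test method fingerstick or venous draw. Entry to Analysis 8: graded from a glucose value with test method Other (SAP 11.8.1.1 and Table 6).
- Analysis 15, ADA severe: third-party intervention = Yes, no test-method condition.

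Result by event type, using 2.5 mmol/L as an example value where glucose was measured:

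| Test method | Third-party help | ADA grade | In Analysis 7 | In Analysis 8 | ADA severe in Analysis 15 |
|---|---|---|---|---|---|
| Fingerstick or venous | Yes | 3 | Yes | No | Yes |
| Fingerstick or venous | No | 2 | Yes | No | No |
| Other | Yes | 3 | No | Yes | Yes |
| Other | No | 2 | No | Yes | No |
| None | Yes | 3 | No | No | Yes |
| None | No | none | No | No | No |

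Two rows matter.

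1. No test method, third-party help: the event is Grade 3 by Table 8 and is counted in Analysis 15, but no rule admits it to Analysis 7 or 8.
2. Test method Other, third-party help: the event is Grade 3 but appears only in Analysis 8. Take a subject with one Grade 1 fingerstick event and one assisted event recorded under Other. That subject's maximum is Grade 1 in Analysis 7 and Grade 3 in Analysis 8. Neither table is built to give the maximum over all of a subject's events, and adding the two tables counts this subject twice.

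Size of the first effect: the documents give no share of assisted events without glucose. Call it u, as an assumption. Of every 10 ADA-severe events, Analyses 7 and 8 together can show 10 × (1 − u) as Grade 3:

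| u | Shown as Grade 3, per 10 |
|---|---|
| 0% | 10 |
| 10% | 9 |
| 20% | 8 |
| 30% | 7 |
| 50% | 5 |

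The range includes no effect at all.

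**The case against.** The strongest reply is that severe hypoglycemia is already reported in full elsewhere. This stands. Analyses 9 and 15, the overall TEAE summary and the listing would carry an assisted event with a completed Hypoglycemia page, whether or not glucose was measured. A reader might infer from the gap that severe events are missing from the safety report; the documents do not support that.

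Second, the gap depends on the CRF and the table shells, which are separate documents. The CRF may not allow a blank test method, Other may absorb unmeasured events, or the shells may include a row for missing values. This also stands, and is why the number affected is unknown. It does not remove the second effect, which needs only an assisted event recorded under Other.

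Third, Analysis 7 is labelled as a subset, so a count that differs from Analysis 15 is no contradiction in itself. This stands in part. The label explains why Other events sit in Analysis 8. It does not explain why an event that meets Grade 3 belongs to neither table, or why a maximum ADA grade should leave out a subject's assisted event.

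Two further inferences go too far. One is that a few omissions would change the comparison between arms: no test or confidence interval is planned on Analyses 7 and 8. The hypoglycemia event-rate model (Analysis 14) and the interaction models for severe hypoglycemic events in SAP 11.8.1 are not tied to test method. The other is that every ADA-graded output is affected: the summary of ADA-graded events by eligibility-deviation subgroup (Analysis 16) states no test-method restriction.

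**Conclusion.** The point holds as a minor inconsistency confined to Analyses 7 and 8. On the SAP's wording, an event can satisfy ADA Grade 3 and be admitted to neither table, and an assisted event recorded under Other is left out of the subject's maximum ADA grade in Analysis 7. Grade 3 in these descriptive tables can therefore be lower than the ADA-severe count in Analysis 15.

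The size cannot be determined from the documents and may be zero. The conclusion assumes a literal reading of the entry rules. The first effect also assumes that the CRF lets an assisted event be recorded without a glucose value or test method. It would be tempting to add that the shortfall falls on exactly those subjects who were too unwell to be tested. That is conjecture; nothing in the documents says why a reading would be absent. No primary or key secondary conclusion is touched.

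**What to change.** Keep the split by test method for the CTCAE tables (Analyses 5 and 6), where grades rest on glucose alone.

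For ADA grade, replace the two tables with one that shows each subject's maximum grade over all hypoglycemic TEAEs with a completed Hypoglycemia page:
- Grade 3 from the third-party answer, whatever the glucose value or test method.
- Grades 1 and 2 from the glucose value, subdivided by test method if wanted.
- A separate row for non-severe events with no glucose value.

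Amend the Table 6 titles for Analyses 7 and 8 to match. Moving every assisted event into Analysis 7 while leaving Analysis 8 and the titles alone would not do: events recorded under Other would appear as Grade 3 twice, and Analysis 7 would contradict its own title. With the single table, each event is counted once, and Grade 3, taken over all preferred terms, agrees with the ADA-severe count in Analysis 15.

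The cost is one derivation change and revised titles and shells. Table 8's definition of the grades is unchanged, and no new data are needed. If no affected events exist, no Grade 3 event is added and the only change is that the two tables become one.
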